6.6.3 Hospital and Provider Characteristics

- Hospital region (Midwest, northeast, south, west)
- Location (urban hospital; rural hospital)
- Hospital setting (inpatient; outpatient)
- Hospital bed size category (small, medium, large): modified from the bed size category definition using region of the U.S., the urban-rural designation of the hospital, in addition to the teaching status (https://www.hcup-us.ahrq.gov/db/vars/hosp_bedsiz/nisnote.jsp)
- Teaching status (teaching hospital; non-teaching hospital)

- Surgeon specialty (colon/rectal surgeon, general surgeon, other, and unknown)

6.7 Subgroups/Stratification Variables

Whether a diverting stoma is an effective and safe procedure to prevent anastomosis leakage in colorectal resections remains controversial. Some studies have reported that the stoma creation reduced the incidence of AL or the AL-related complications, such as pelvic abscess.¹⁴⁻¹⁶ To minimize the impact of an elective diverting stoma on the AL risk estimate, secondary analyses will be conducted separately in those with and without a diverting stoma procedure prior to or on the same day as the index procedure (i.e., left-sided colorectal surgery) during the index admission.

6.8 Sample Size and Study Power

A feasibility analysis identified more than 10,000 patients in PHD between 2019 and 2021 who were treated surgically with the use of Ethicon Manual Circular Stapler. Among those, approximately 6,000 patients had a left-sided colorectal surgery.

Among approximately 13,000 patients who were treated surgically with Medtronic EEA™ Circular Stapler with DST Series™ Technology, about 6,000 patients had a left-sided colorectal surgery in the PHD.

A similar analysis identified 623 patients in PHD between 2019 and 2021 who underwent surgical procedures where Medtronic EEA™ Circular Stapler with Tri-Staple™ Technology was used. Among those, 526 underwent a left-sided colorectal surgery.

The final sample sizes for the study will vary based on applying the inclusion and exclusion criteria, as well as additional data beyond 2021 being available from PHD.

Power estimates assuming different combinations of relative risk, sample size, and the cumulative incidence of AL in the comparison cohort—Medtronic EEA™ Circular Stapler with Tri-Staple™ Technology— are provided in [Table 2](#)

[Table 2.](#) The calculations assumed one-sided tests at a significance level of 0.025 (or type I error of 0.025). The estimated cumulative incidence of AL among patients who underwent a colorectal surgery with the use of Medtronic EEA™ Circular Stapler with Tri-Staple™ Technology ranges from 2% to 3.5% in the literature.^{8,12}

[Table 2: Power estimation, by relative risk](#)

Relative Risk	AL risk in the comparison cohort	Sample size in the target cohort	Sample size in the comparison cohort	Power
2.5	3%	6,000	500	0.995
2	3%	6,000	500	0.856
1.5	3%	6,000	500	0.324
2.5	2%	6,000	500	0.938
2	2%	6,000	500	0.642
1.5	2%	6,000	500	0.209

6.9 Data Analysis

6.9.1 Primary Descriptive analysis

6.9.1.1 Demographic, clinical, and procedural characteristics

Descriptive analyses will be first performed for demographic, clinical, and procedural characteristics of patients at the time of the index procedure where a study device was used. Descriptive statistics will be calculated for all study cohorts, including pre- and post- weighted patients by study device. Categorical variables will be summarized by frequencies and proportions and continuous variables will be summarized by means and standard deviations or medians and interquartile ranges. Balance is evaluated using absolute standardized differences (ASD). Nominal variables with more than two categories are summarized using a generalization of the absolute standardized difference for binary covariates. See the expected outputs in [Table B- 1](#), [Table B- 2](#), [Table B- 3](#), [Table B- 4](#), and [Table B- 5](#))

6.9.1.2 Unadjusted Cumulative incidence of AL

The number of new cases of AL within 30 days post-index procedure will be determined via surrogate diagnoses which usually occur concomitantly with a leak, e. g. an abscess, peritonitis or a fistula or the presence of a procedure code indicating diverting stoma— a surgical treatment for severe AL [defined in Section [6.5 Dependent Variables \(Outcomes\)](#)]. Unadjusted cumulative incidences [(number of new cases/number of patients at risk during the specified time period) x 100] and 95% CI will be calculated for all study cohorts. Cumulative incidences of AL and 95% CIs will also be stratified by key characteristics (including demographic, clinical, procedural, hospital, and provider characteristics). See the expected outputs in [Table B- 6](#), [Table B- 7](#) and [Table B- 8](#).

6.9.2 Primary Comparative analysis

The goals of comparative analyses are to: 1) estimate the RR of AL for Ethicon Manual Circular Staplers compared to Medtronic EEA™ Circular Stapler with Tri-Staple™ Technology; 2) estimate the RR of AL for the Medtronic EEA™ Circular Stapler with DST Series™ Technology compared to Medtronic EEA™ Circular Stapler with Tri-Staple™.

The primary analyses will be conducted separately for the comparison between Ethicon Manual Circular Stapler versus Medtronic EEA™ Circular Stapler with Tri-Staple™ Technology and the comparison between Medtronic EEA™ Circular Stapler with DST™ Technology and Medtronic EEA™ Circular Stapler with Tri-Staple™ Technology. See the expected outputs in [Table B- 7](#) and [Table B- 8](#).

A propensity score weighting (PSW) method will be used to control for potential confounders by balancing the distribution of baseline demographic, clinical, and procedural characteristics between the comparison groups. The following baseline variables will be considered in the propensity score model based on their clinical relevance to the safety of the device: patient demographics (age, sex, and race), clinical characteristics (CCI, comorbid conditions, diverting stoma occurred prior to or on the same day as the index procedure), procedural characteristics (procedure year, surgical site, primary diagnosis, surgical approach, and admission type), and hospital and provider

RWE23-SAF-001:Comparative safety study to assess the risk of AL of 2-row vs 3-row circular staplers

characteristics (hospital region, hospital location, hospital setting, hospital bed size, and surgeon specialty).

The weighting will be carried out for the comparator group to make it comparable in propensity score to the target group. Two propensity score weighting methods— untrimmed and trimmed— can be used to balance the data to make the target group and the comparison group comparable on the measured confounders. The choice among the methods will be based on which provided the best balance. Propensity score methods that estimate the average treatment effect on the treated will be calculated and will be compared on the basis of covariate balance as measured by the absolute standardized difference (ASD), which is the difference in means or proportions expressed in pooled standard deviation units. We will compare the approaches on the basis of the number of variables with an ASD of >0.10 and the mean ASD, and the weighting approach with the fewest number of variables with covariate imbalance will be selected for analysis. If two methods achieve the same minimum number of variables with covariate imbalance, the method with the smallest ASD across all variables will be selected for outcome analysis. Notably, one data analyst will balance the data without access to the outcome data and a separate individual will perform the outcome analysis using the balanced data, thus removing the potential for bias resulting from repeated applications of covariate balancing to obtain a desired study outcome.

In the final PSW cohorts, covariate balanced cumulative incidences and 95% CI will be calculated for all device cohorts. A weighted (covariate balance weights) log-binomial regression outcome will be used with treatment as the only explanatory variable to estimate the covariate balanced RR (target group versus the comparator group for the study outcome of interest). A cluster robust standard error approach will be applied to calculate the variability in the estimate and to construct two-sided 95% confidence intervals. All variables included in the propensity score model are prespecified confounders of the relationship between the circular stapler and AL. If any of those variable don't balance well through propensity scores, it will be added as a covariate in the log-binomial regression model.

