6. RESEARCH METHODS

6.1 Data Source(s)

This study will use hospital billing records contained in the Premier Healthcare Database (PHD). The PHD contains complete clinical coding, hospital cost, and patient billing data from more than 1,041 hospitals throughout the United States (US). The PHD represents approximately 25% of inpatient hospital stays in the US, and it includes a wide variety of regions and most healthcare insurances in the US. Premier collects data from participating hospitals in its health care alliance. The Premier Alliance was formed to improve the quality of care. Participation in the Premier Alliance is voluntary. Although the database excludes federally funded hospitals (e.g., Veterans Affairs), the hospitals included are nationally representative. The database contains a date-stamped log of all billed items by cost-accounting department including medications; laboratory, diagnostic, and therapeutic services; and primary and secondary diagnoses for each patient's hospitalization. Identifier-linked enrollment files provide demographic and payor information. Detailed service level information for each hospital day is recorded; this includes details on medication and devices received.¹³

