8 LIMITATIONS OF RESEARCH METHODS

The study is observational in nature and thus susceptible to limitations.

The first relates to the validity of the diagnosis of anastomotic leak. As with any other non-interventional database study using health insurance administrative claims or electronic health records (EHR), identification of medical events, such as anastomotic leak or co-morbidities, is limited to data that are captured as part of the medical record or claims, which are not primarily collected for research purposes, and will rely on appropriate diagnostic codes to detect these events. As there is no specific diagnosis code for anastomotic leak in the ICD-10-CM taxonomy, the anastomotic leak surrogate diagnoses, such as abscess of intestine, fistula of intestine, peritonitis, or peritoneal abscess, will be used to define AL in the PHD. Misclassification bias can result if study patients are not categorized correctly with regards to outcome, however, should be non-differential between the comparison groups.

Misclassifications due to the secondary use of billing data may also lead to under or overestimation of cohort size. For example, the search strategy designed in this study may underestimate the prevalence of products in the database if the search strategy missed any incorrectly coded entries for study devices such as misspellings leading to misclassification of the exposure. However, there is no evidence that the misclassification bias would be differential between the comparison groups.

Indication for product usage is not specifically stated in the PHD; it is being inferred based on the primary procedure codes recorded during the index hospitalization. Therefore, misclassification of indication in this study is possible but should be non-differential between the comparison groups.

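### The propensity score omits hospital case volume and teaching status, and no planned analysis compares devices within hospitals, so hospital-level differences could bias both primary relative risks

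*Supplement*

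**What the plan says.** Section 6.9.2 gives the hospital and provider terms of the propensity score as "hospital region, hospital location, hospital setting, hospital bed size, and surgeon specialty". The list is final rather than deferred to another document: "All variables included in the propensity score model are prespecified confounders of the relationship between the circular stapler and AL".

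The adjusted estimate comes from a weighted model: a "log-binomial regression outcome will be used with treatment as the only explanatory variable". The one exception is that a score variable that stays unbalanced may be added as a covariate, and that route cannot reach a variable outside the score. On clustering, the section says "A cluster robust standard error approach will be applied to calculate the variability in the estimate" and does not name the cluster.

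Section 6.6.3 defines teaching status, and the patient-characteristics tables (B-2 to B-5, C-1 to C-8) show it by device, but 6.9.2 does not list it. Hospital volume, surgeon volume and hospital identity do not appear in sections 6.6.1 to 6.6.3, in 6.9.2, in the mock-up tables or in section 8. The only sensitivity analysis (6.9.4) concerns 30-day hospital enrollment.

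On the outcome, section 8 states: "Misclassification bias can result if study patients are not categorized correctly with regards to outcome, however, should be non-differential between the comparison groups".

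**The concern.** Staplers may be bought by the hospital or preferred by the surgeon, not allocated patient by patient. If so, device and hospital travel together, and whatever else differs between hospitals travels with the device. Two such differences matter here.

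- **Leak risk.** Hospitals and surgeons may differ in skill and experience in ways that bed size and specialty capture only in part.
- **Ascertainment.** Sections 6.5 and 8 say that there is no specific diagnosis code for anastomotic leak, so the outcome rests on surrogate codes. Table A-2 includes broad entries such as K91.89 and Y83.2, whose use may depend on local coding practice. Section 8 adds that care at a different hospital is not linked to the index patient, so capture after discharge also depends on the hospital.

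Both primary comparisons use the same Tri-Staple cohort, so a peculiarity of the few hospitals behind it would enter both relative risks. The result could then partly reflect which hospitals used which device. As written, section 8 would lead a reader to dismiss that possibility.

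**Working it through.** **1. The plan's own figure.** Table 2 (section 6.8) reproduces with a pooled-variance z-test of two proportions, 6,000 against 500 patients, one-sided 0.025:

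power = Φ[(q − p − 1.96·s0)/s1], where p is the comparator risk, q = RR·p, s0 the pooled and s1 the unpooled standard error.

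For RR 2 at 3%: s0 = 0.01085, s1 = 0.00822, (0.03 − 1.96 × 0.01085)/0.00822 = 1.06, power 0.856. All six rows match: 0.995, 0.856, 0.324, 0.938, 0.642, 0.209. The calculation treats patients as independent and leaves no room for hospital-level bias.

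**2. What each element of the plan can do about a hospital-level confounder.**

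| Element | Effect |
|---|---|
| Region, location, setting, bed size, specialty in the score | Partial proxies; remove only the part correlated with them |
| Fallback covariates | Only variables already in the score |
| Cluster-robust standard error | Changes the interval, not the estimate |
| 30-day enrollment sensitivity analysis | Addresses loss to follow-up |
| Table B-6 strata (region and setting among them) | Descriptive incidence by device; not within hospital |

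**3. Comparator events.** Section 6.8 says of the Tri-Staple patients: "Among those, 526 underwent a left-sided colorectal surgery". It gives a literature risk of 2% to 3.5%.

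- 526 × 0.02 = 10.5; 526 × 0.035 = 18.4, so about 11 to 18 events.
- With 6,000 target patients at the same risk, SE(log RR) = √(1/e0 − 1/526 + 1/e1 − 1/6000), where e0 and e1 are the comparator and target events.
- At 2%: √(1/10.52 − 1/526 + 1/120 − 1/6000) = 0.318; exp(1.96 × 0.318) = 1.87.
- At 3.5%: √(1/18.41 − 1/526 + 1/210 − 1/6000) = 0.239; exp(1.96 × 0.239) = 1.60.
- The unweighted 95% limits therefore lie a factor of 1.60 to 1.87 either side of the estimate, and almost all of this comes from the comparator events.

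**4. What the hospital count does and does not show.** Section 6.1 describes "patient billing data from more than 1,041 hospitals throughout the United States". At most 526/1,041 = 50.5% of these can hold a comparator patient in the 2019–2021 feasibility data. Random scatter would reach about 1,041 × [1 − (1 − 1/1,041)^526] = 413 hospitals. The count thus follows from the small cohort alone and is not evidence of clustering.

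**5. Illustrations on assumed inputs.** None of these inputs is in the documents; they show mechanism and direction, not expected size.

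- *Coding.* If comparator hospitals record the surrogates 10% to 30% more often, a true RR of 1.5 appears as 1.5/1.1 = 1.36 to 1.5/1.3 = 1.15. If 10% to 30% less often, as 1.5/0.9 = 1.67 to 1.5/0.7 = 2.14.
- *Volume.* Suppose low-volume providers carry 1.25 to 2.0 times the leak risk and treat 50% to 70% of target but 20% to 30% of comparator patients, with none of this removed by weighting. A true RR of 1 then appears as (1 + 0.25 × 0.5)/(1 + 0.25 × 0.3) = 1.05 up to (1 + 1 × 0.7)/(1 + 1 × 0.2) = 1.42. At 3% comparator risk and the Table 2 sample sizes, one-sided rejection would be 3.4% to 24.0% against a nominal 2.5%.

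**6. Precision of an analysis in hospitals using both devices.** The overlap is not given. If half the comparators (263) were in such hospitals, 263 × 2% to 3.5% gives 5.3 to 9.2 events. Using 1/√events as the approximate standard error and ignoring the target arm, the 95% factor is exp(1.96/√5.26) = 2.35 to exp(1.96/√9.205) = 1.91.

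**The case against.** The strongest reply is that the case for clustering is not in the documents. No section says that staplers are chosen by hospital or surgeon, and neither the number of comparator hospitals nor their overlap with target hospitals is reported. A reader might infer from 526 patients in more than 1,041 hospitals that comparator use is concentrated. Step 4 shows why that does not follow. The 1,041 is also every hospital in the database, not those doing this surgery, and the study window runs past 2021. This objection stands in full.

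Second, every bias figure is assumed, and the assumptions can be set to push either way. The volume illustration treats the whole imbalance as residual, although the listed covariates would absorb some of it. A spurious RR of 1.05 to 1.42 also lies within the sampling factor in step 3. This stands as a limit on what can be said about size.

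Third, the plan is not blind to site. Bed size is defined using region, urban-rural designation and teaching status; specialty separates colon/rectal from general surgeons; and the descriptive tables show hospital characteristics by device. These are partial safeguards, so it would be too strong to say that nothing planned could hint at a problem. None of them compares devices within a hospital or brings volume into the adjustment.

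Finally, restricting to hospitals that used both devices would not suffice. A pooled analysis there still mixes hospitals with different device shares, so the analysis must also condition on hospital.

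**Conclusion.** The gap is real and should be closed. Hospital case volume and teaching status are outside a covariate list that the plan fixes, no analysis compares devices within hospitals, and the cluster-robust standard error does not address bias. Section 8's assurance on outcome misclassification has no support at hospital level.

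Whether this biases the result depends on device choice following hospital or surgeon, and on those hospitals differing in leak risk or coding. Both are plausible and neither is documented. Direction and size cannot be derived from the documents. What can be said is that about 11 to 18 expected comparator events make the estimates sensitive to a few hospitals.

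A reader might go further and conclude that the comparator is shown to be concentrated in few hospitals, or that the planned comparison is invalid. The documents support neither. This is an unexamined source of residual confounding that can be partly checked, not a demonstrated bias.

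**What to change.** 1. In 6.9.2, add hospital annual left-sided colorectal volume (Table A-1 encounters per hospital-year) and teaching status to the propensity list, and add volume to the balance tables. Add surgeon volume only if the database holds a provider key; the documents do not say that it does.
2. Report how many hospitals contribute to each device cohort and how far they overlap. Add to Tables B-7 and B-8 a sensitivity row limited to hospitals that used both devices in that comparison and conditioned on, or stratified by, hospital. Label it supportive because of its wide interval.
3. In section 8, replace the assertion of non-differential outcome misclassification with a statement that it may differ by hospital and hence by device, and that item 2 examines this only partly.

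**Cost.** Volume is a count from codes already listed, and section 8 says that records are linked within institution. The primary estimand is unchanged. The downsides are a few more score terms on a comparator cohort of about 500 and low precision in the new row: on the assumed half overlap, limits a factor of roughly 1.9 to 2.4 either side. That row can flag a gross discrepancy but cannot confirm the primary result.

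### Teaching status is defined and tabulated for balance, but it is the only hospital or provider variable left out of the propensity list, so it is not directly adjusted

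*Supplement*

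**What the plan says.** Section 6.6.3 lists region, location, setting, bed size, teaching status and surgeon specialty. Teaching status has two levels: "Teaching status (teaching hospital; non-teaching hospital".

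Section 6.9.2 introduces the propensity variables with "The following baseline variables will be considered in the propensity score model based on their clinical relevance to the safety of the device". For hospitals and providers it then names "hospital region, hospital location, hospital setting, hospital bed size, and surgeon specialty". Teaching status is not among them.

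The outcome model that follows is a weighted "log-binomial regression outcome will be used with treatment as the only explanatory variable". Section 6.9.2 then states: "All variables included in the propensity score model are prespecified confounders of the relationship between the circular stapler and AL". The next sentence gives the remedy for poor balance: "If any of those variable don't balance well through propensity scores, it will be added as a covariate in the log-binomial regression model".

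The choice between trimmed and untrimmed weights is made "on the basis of the number of variables with an ASD of >0.10 and the mean ASD".

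Tables B-2 to B-5 and C-1 to C-8 each carry a teaching-hospital row under an ASD column.

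**The concern.** The plan treats teaching status as a characteristic whose balance is worth checking, but provides no step that acts on the result. An analyst following 6.9.2 as written would weight without it. If it stayed unbalanced, the analyst would report the imbalance and then fit a model with treatment as the only term.

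The comparison cohort is small: 526 Tri-Staple patients with left-sided surgery, against about 6,000 in each target cohort (section 6.8). If the use of that device differs by type of hospital, and leak risk or its coding also differs by type of hospital, part of the adjusted relative risk would reflect the hospital and not the stapler. Sections 6.9.3 and 6.9.4 repeat the primary analysis, so the omission carries into the stoma strata and the sensitivity analysis.

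**Working it through.** **1. Variable lists side by side.** Counting comorbid conditions as one item:

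| Section | Variables defined | In the 6.9.2 list |
|---|---|---|
| 6.6.1 | 5 (age, sex, race, Charlson index, comorbid conditions) | 5 |
| 6.6.2 | 6 (site, primary diagnosis, diverting stoma, approach, year, admission type) | 6 |
| 6.6.3 | 6 (region, location, setting, bed size, teaching status, surgeon specialty) | 5 |
| Total | 17 | 16 |

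Teaching status is the only one of the 17 not carried over.

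**2. Reach of the residual-imbalance rule.** The rule refers back to the variables in the propensity model. Teaching status is not one of them, so the rule does not reach it. The rule states no cut-off of its own; I use the 0.10 that 6.9.2 applies when choosing the weights. An ASD above 0.10 for teaching status would appear in the post-weighting tables (B-4, B-5, C-3, C-4, C-7, C-8) and nothing in the text would follow from it.

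**3. Possible size.** The documents give no teaching-hospital proportion by device and no association with leak. Every input in this step is an assumption. Let p1 and p0 be the teaching proportions in the target and weighted comparison cohorts, and g the leak risk ratio for teaching versus non-teaching hospitals.

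- ASD = |p1 − p0| / sqrt{[p1(1 − p1) + p0(1 − p0)] / 2}
- Factor on the relative risk = [1 + p1(g − 1)] / [1 + p0(g − 1)]

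Example with p1 = 0.40, p0 = 0.50, g = 1.5: ASD = 0.10 / sqrt[(0.24 + 0.25)/2] = 0.20; factor = 1.20/1.25 = 0.96.

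| p1 | p0 | ASD | g = 1.2 | g = 1.5 | g = 2.0 |
|---|---|---|---|---|---|
| 0.40 | 0.45 | 0.10 | 0.991 | 0.980 | 0.966 |
| 0.40 | 0.50 | 0.20 | 0.982 | 0.960 | 0.933 |
| 0.40 | 0.60 | 0.41 | 0.964 | 0.923 | 0.875 |
| 0.40 | 0.70 | 0.63 | 0.947 | 0.889 | 0.824 |

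If the two proportions are swapped between cohorts, each factor becomes its reciprocal (1.009 to 1.214 over the table).

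**4. Scale against sampling error.** The plan has no figure for this point, but Table 2 gives sample sizes and risks. A one-sided 0.025 test with pooled variance and a normal approximation reproduces all six of its powers. For a relative risk of 2 at 3%:

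- Pooled risk = (15 + 360)/6,500 = 0.0577
- Null SE = 0.01085; alternative SE = 0.00822
- (0.03 − 1.96 × 0.01085)/0.00822 = 1.06, so power = 0.856, as stated

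With the same inputs, before any loss from weighting or clustering:

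- Comparison risk 3%: SE(log RR) = sqrt(0.97/15 + 0.94/360) = 0.26; the 95% limits are the estimate multiplied or divided by exp(1.96 × 0.26) ≈ 1.7.
- Comparison risk 2%: SE(log RR) = sqrt(0.98/10 + 0.96/240) = 0.32; the corresponding factor is about 1.9.

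The 0.96 example is a log shift of 0.041, or 0.13 to 0.16 of one SE. The most extreme cell, 0.824, is a log shift of 0.194, or 0.61 to 0.75 of one SE.

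**The case against.** Several points on the other side have weight.

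- **Indirect balance.** Region, location, bed size and surgeon specialty are weighted on, and section 6.6.3 describes the bed-size category as derived partly from teaching status. These may balance teaching status in part. A reader might infer that it is left wholly uncontrolled; the documents do not support that. What stands is that it is not directly adjusted and that there is no remedy if the indirect balance fails.
- **Choice of weights.** A reader might also infer that teaching status plays no part in choosing between trimmed and untrimmed weights. Section 6.9.2 does not restrict the ASD count to propensity variables, and the tie-break refers to all variables, so teaching status may already count there. It would still enter neither the propensity model nor the outcome model.
- **Bed size.** It is tempting to add that the bed-size categories are not comparable unless teaching status is in the model. The cut-offs actually used are not shown, and one main-effect term would not change what a size category means in each type of hospital. That argument is not relied on here.
- **Confounding is not shown.** Section 4 does not name teaching status among the leak risk factors, and describing a variable does not oblige anyone to model it. That is fair. Yet the other five hospital and provider variables were accepted under the same clinical-relevance criterion, and no reason is given for treating this one differently.
- **Flexibility.** The variables are only to be considered, which might seem to leave room to add one. But the plan relies on its confounders being prespecified, and a variable added later would not be.
- **Visibility.** Any imbalance would be open to readers in the post-weighting tables. That is true, but showing an imbalance does not correct the estimate.

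**Conclusion.** The omission is plain on the text and may be a drafting slip. Teaching status is not directly adjusted, and a residual imbalance would be shown without triggering adjustment.

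The documents do not show that the relative risk will be biased, or in which direction. Under the assumed inputs the factor lies between 0.97 and 0.99 at an ASD of about 0.10, and reaches 0.82 only with an ASD of about 0.63 and a doubled leak risk by hospital type (or the reciprocals). Any bias is therefore likely to be modest unless the residual imbalance is large. Table 2 is unaffected. The change is worth making because it removes an avoidable source of possible confounding at almost no cost, not because a material error has been shown.

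**What to change.** Add teaching status, as one indicator, to the hospital and provider variables in the propensity list of section 6.9.2. The residual-imbalance rule then covers it without further wording. If the sponsor prefers to leave it out, the section should give the reason, or the rule should be extended to every variable in the balance tables.

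The cost is one phrase in the protocol and one more term in each propensity model. The variable is already defined in 6.6.3 and already has a row in every balance table, so no new data and no new tables are needed.

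### Both primary confidence intervals rest on a cluster-robust standard error with no named cluster and no few-cluster correction, so their coverage is not assured for a small, weighted comparator arm

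*Supplement*

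**What the plan says.** Section 6.9.2 (Primary Comparative analysis) fits a weighted model in each of the two comparisons: "log-binomial regression outcome will be used with treatment as the only explanatory variable to estimate the covariate balanced RR". The interval comes from one sentence: "A cluster robust standard error approach will be applied to calculate the variability in the estimate and to construct two-sided 95% confidence intervals". No cluster unit (hospital, surgeon or patient), small-sample correction, reference distribution or minimum number of clusters is given.

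The weights fall on the small arm: "The weighting will be carried out for the comparator group to make it comparable in propensity score to the target group". Section 6.8 gives the sizes. For Ethicon: "Among those, approximately 6,000 patients had a left-sided colorectal surgery". For DST: "about 6,000 patients had a left-sided colorectal surgery in the PHD". For Tri-Staple: "Among those, 526 underwent a left-sided colorectal surgery". These are feasibility counts, and the section adds: "The final sample sizes for the study will vary based on applying the inclusion and exclusion criteria".

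Section 6.1 puts the database at over 1,041 hospitals. Nothing in the protocol says how many of them contribute Tri-Staple patients, and mock Tables B-1, B-7 and B-8 have no place for that number. The one sensitivity analysis (Section 6.9.4) concerns 30 days of hospital enrolment, not variance.

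**The concern.** A sandwich variance relies on many clusters in each group being compared. What counts here is the number of hospitals behind the Tri-Staple arm, because that arm dominates the variance. With few such hospitals, or a few large ones, the estimated standard error is too small on average, and a normal quantile makes no allowance for its own uncertainty. Uneven weights reduce the information further. Software defaults do not help, because their correction uses the total number of clusters.

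The primary results are two relative risks with 95% intervals in a safety comparison. An interval that is too narrow can make chance look like a 2-row excess, or like reassurance about the 2-row devices. Both comparisons use the same Tri-Staple patients, so both intervals share the weakness, and agreement between them is not independent confirmation. Section 6.9.3 repeats the method within stoma strata, where the comparator arm is smaller still.

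**Working it through.** **Plan's own figure.** Table 2 reproduces exactly with a pooled-variance test, one-sided 0.025, independent patients, 6,000 vs 500. For relative risk 2 at 3%:
- pooled risk = (500×0.03 + 6,000×0.06)/6,500 = 0.0577
- null SE = √[0.0577×0.9423×(1/500 + 1/6,000)] = 0.01085
- alternative SE = √[0.03×0.97/500 + 0.06×0.94/6,000] = 0.00822
- power = Φ[(0.03 − 1.96×0.01085)/0.00822] = Φ(1.06) = 0.856, as printed.

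The other five entries also agree, so no stated figure is wrong.

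**Share of the variance.** With equal risks and weights, the comparator's share of Var(log RR) is (1/500)/(1/500 + 1/6,000) = 0.923; with 526 it is 6,000/6,526 = 0.919. If the weights had a coefficient of variation (CV) of 1 (assumed), the effective comparator size would be 526/(1 + 1²) = 263 and the share 6,000/6,263 = 0.958.

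**Why the default factor does not help.** The common correction (CR1) multiplies the variance by G/(G − 1), with G the total number of clusters. With 10 comparator and 200 target hospitals this is 210/209 = 1.005. A factor based on the comparator hospitals alone would be 10/9 = 1.111.

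**Simulation, true relative risk 1.** Section 6.8 supplies 526 vs about 6,000 patients and the 3% risk. Everything else is assumed: 10-80 comparator hospitals, 200 target hospitals, one device per hospital, unequal hospital sizes (CV about 1), intracluster correlation 0.01-0.03, comparator weights equal or with CV 1, and a 10% leak risk as an alternative. There were 4,000 runs per cell, so the Monte Carlo error of a coverage near 0.90 is √(0.9×0.1/4,000) = 0.005.

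Cells show the percentage of uncorrected sandwich intervals (CR0, normal quantile) wholly above 1 / wholly below 1 (nominal 2.5 / 2.5), then coverage = 1 − their sum.

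| Leak risk, weights, ICC | 10 hospitals | 20 | 40 | 80 |
|---|---|---|---|---|
| 3%, CV 1, 0.03 | 9.8 / 6.2; 0.840 | 6.8 / 4.0; 0.892 | 5.5 / 3.0; 0.915 | 5.0 / 2.5; 0.925 |
| 10%, CV 1, 0.03 | 8.1 / 7.0; 0.849 | 5.3 / 4.9; 0.898 | 4.2 / 4.4; 0.914 | 3.5 / 3.1; 0.934 |
| 10%, equal, 0.03 | 7.8 / 6.4; 0.858 | 5.3 / 4.3; 0.904 | 3.1 / 3.7; 0.932 | 2.4 / 3.1; 0.945 |
| 10%, equal, 0.01 | 5.7 / 6.2; 0.881 | 4.5 / 4.5; 0.910 | 3.2 / 3.5; 0.933 | 2.5 / 3.4; 0.941 |

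In the cells shown, CR1 changes a tail by at most 0.2 points. At 3% risk, mean estimated SE over true SD is 0.70-0.80 with 10 hospitals, 0.83-0.88 with 20, 0.88-0.95 with 40 and 0.90-0.94 with 80. At 3% with equal weights and 40-80 hospitals, the upper tail is 2.4-3.2%.

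**If the patient were the cluster.** At 3%, weight CV 1 and ICC 0.03, unclustered intervals miss 12.1 + 10.6 = 22.7% of the time with 10 hospitals and 7.6 + 5.1 = 12.7% with 40. The unnamed unit therefore matters.

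**Does a correction work?** A second simulation with CR1 and a normal quantile gave coverage of 0.85-0.88 at 10 hospitals, 0.89-0.91 at 20, and 0.91-0.94 at both 40 and 80. A leave-one-hospital-out jackknife with t on comparator hospitals minus 1 gave 0.93-0.96 in every cell. A simpler repair (comparator-only factor plus the same t) was better than the default but not nominal: at 20 hospitals and 3% risk its upper tail was 3.1-5.5%. CR2 with Satterthwaite degrees of freedom was not simulated.

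**The case against.** The strongest reply is that this is an unspecified detail and not a wrong choice. CR2, a jackknife or t-based limits would all satisfy the sentence in Section 6.9.2, and a correction factor is often left to a separate analysis plan. A reader might infer that the sponsor will use the standard form; the text does not say so.

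A reader might also infer that the Tri-Staple patients do come from a handful of hospitals. The documents do not support that: 526 patients in a database of this size could come from 80 hospitals or more, and the count may change with data beyond 2021. With 40 or more hospitals and equal weights, the shortfall is small.

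A third tempting reading is that the error favours a finding of 2-row harm. It does not do so consistently. The upper tail is larger in the 3% row above, but a further run at 3% risk with equal weights put false benefit ahead of false harm (6.6% vs 5.3% with 10 hospitals, 3.9% vs 3.1% with 40). Section 5.2.1 also sets estimation objectives, with no decision rule for declaring an excess.

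All of this stands as a limit on the claim. It does not remove the gap: this document carries the analysis section and the mock tables, its only variance statement leaves open choices that affect coverage, and no planned output would let a reader judge the result.

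**Conclusion.** The point holds as a conditional weakness in the method for both primary intervals; it is not a demonstrated error in them. If the usual sandwich with a normal quantile is used, a nominal 95% interval covers about 0.85-0.88 of the time with 10 comparator hospitals, 0.89-0.91 with 20 and 0.91-0.94 with 40-80. The low end arises mostly when the weights vary (CV 1), and the misses fall in both tails. One cell in the table, at 0.840, lies just below the first range.

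These figures rest on assumed hospital counts, size spread, intracluster correlation, weight spread and one device per hospital. The documented parts are the missing specification, the roughly 92% variance share and the placement of the weights on the small arm. The change is worth making because it is cheap and a better-performing method is available.

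**What to change.** In Section 6.9.2:
- Name the hospital as the cluster.
- Prespecify a leave-one-hospital-out jackknife variance with a t reference on comparator hospitals minus 1, or a bias-reduced sandwich (CR2) with Satterthwaite degrees of freedom. The jackknife is the option whose coverage was checked here. If it is chosen, say whether the propensity score is refitted in each replicate and what is done if a replicate leaves no comparator events.
- Carry the same rule into the stoma-stratified analyses.

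In Tables B-7 and B-8, print the number of comparator hospitals and the largest hospital's share beside each relative risk. The analyst who balances the data without outcome access can report both before the outcome analysis.

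The work is a few sentences and a few lines of code, with no new data and no change to the point estimates. The price is wider intervals: about 5-11% at 80 comparator hospitals, 8-14% at 40, 15-22% at 20 and 32-37% at 10. The cost is therefore smallest where hospitals prove plentiful.
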